## 5.7 Analysis of secondary outcomes/endpoints

The secondary outcome measures are between group comparison of the change from baseline to 12 months of diabetes incidence and cardiometabolic risk factors.

### 5.7.1 Description of secondary criteria

Variable name and unit	Variable source 	Type 	Set 
Diabetes			
Diabetes incidence after baseline visit during 12 months	R	N	ITT, PP
Change from baseline to 6 and 12 months of cardiometabolic risk factors			
Fasting and 2h glucose (during OGTT) (mmol/L)	D	C	ITT, PP
Fasting and 2h insulin (during OGTT) (mIE/L)	D	C	ITT, PP
Fasting HbA1c (mmol/mol)	D	C	ITT, PP
Fasting cortisol (nmol/L)	D	C	ITT, PP
Fasting ACTH (pmol/L)	D	C	ITT, PP
Fasting Apo A1 (g/L)	D	C	ITT, PP
Fasting ApoB (g/L)	D	C	ITT, PP
Fasting Triglycerides (mmol/L)	D	C	ITT, PP
Fasting LDL (mmol/L)	D	C	ITT, PP
Fasting HDL (mmol/L)	D	C	ITT, PP
C-reactive protein (mg/L)	D	C	ITT, PP
Creatinine (μmol/L)	D	C	ITT, PP
eGFR (mL/min/1,73 m  )	D	C	ITT, PP
BMI (Kg/m  )	D	C	ITT, PP
Waist circumference (cm)	D	C	ITT, PP
Systolic blood pressure (mm Hg)	D	C	ITT, PP
Diastolic blood pressure (mm Hg)	D	C	ITT, PP
Body fat%	D	C	ITT, PP
Other blood laboratory parameters			
Fasting copeptin (pmol/L)	D	C	ITT, PP
Urine laboratory parameters			
Albumin/creatinine ratio (g/mol)	D	C	ITT, PP

1. (R)aw or (D)erived data
2. (C)ontinuous or (O)rdinal or (N)ominal
3. Intention to treat (ITT) or Per Protocol (PP)

### 5.7.2 Analysis of secondary outcome parameters

New-onset diabetes is defined as 2 consecutive fasting plasma glucose values  $\geq 7.0$  mmol/L or 2-hour post OGTT value of  $\geq 11.0$  mmol/L after the baseline exam (V3). In addition, new onset diabetes is considered present if diagnosed by a physician outside of the current study, as assessed in the questionnaire (answering yes on having had a physician diagnosis of diabetes or having been prescribed

medication for diabetes) after the baseline exam (V3). All individuals with a diagnosis of diabetes at or before the baseline exam (V3) will be excluded in the analysis of incidence of diabetes.

The difference in diabetes incidence between the intervention and control group will be analyzed using logistic regression with diabetes incidence as the binary outcome and treatment arm as exposure variable and reported as the odds ratio (OR) including 95 % CI for diabetes incidence in intervention vs control. As the randomization should lead to no difference in diabetes risk factors, the main analysis will only be adjusted for sex (as the randomization is stratified by sex, this covariate will be included in all outcome analyses), but we will also add a sensitivity analysis to adjust for key diabetes risk factors at baseline (fasting glucose, diabetes status, BMI, age), if there is a clinically significant difference in these factors between treatment groups despite the randomization.

Cardiometabolic risk factors will be analyzed using the same method as for the primary outcome, but with baseline value for the actual factor as a covariate instead of baseline value of fasting plasma glucose.

In addition, to assess the possible association between change in fasting plasma glucose levels, copeptin, other cardiometabolic risk factors, other blood laboratory parameters and urine laboratory parameters, we propose to analyze correlation(s) between delta value of outcome parameters and delta value of the efficacy parameters (e.g. urine volume, urine osmolality and plasma copeptin) with Pearson or Spearman correlation analyses.

- Outcome parameters are fasting plasma glucose and all secondary continuous outcome parameters listed in section 5.7.1 above.

We emphasize that in these correlation analyses, copeptin will be regarded both as an outcome parameter and as an efficacy parameter.

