Assessment of outcome and baseline characteristics (TABLE 1): Clinic visits are performed at baseline, 3 weeks, 3, 6, 9 and 12 months at which cardiometabolic risk factors and hydration parameters are measured as detailed in **TABLE 1**. Please note that the main outcome variables are measured at baseline, 6 months and 12 months. The purpose of the other clinic visits is to optimize adherence to the allocated treatment arm. All laboratory analyses will be performed using certified methods. In addition, we will record medication, fluid/water and dietary intake and medical history. The gut microbiota composition has been suggested to mediate systemic metabolic changes. As stool consistency, in turn highly affected by water intake, has been shown to be one of the main factors determining the microbiota composition (Science 2016;352:560-4), we will measure the gut microbiota in order to test if such changes may mediate part of any beneficial effects of water supplementation on metabolism. Stool consistency will be assessed using a Bristol score chart. Furthermore, as recent work shows that genetic factors play a role in determining basal level of VP (measured by copeptin) (J Clin Endocrinol Metab 2016;101:2432-9), it can be hypothesized that the magnitude of the copeptin lowering effect by water – and the potential effects of metabolism – varies according to such genetic factors. Therefore, we will also isolate DNA from buffy coats in order to determine such genetic variation.

TABLE 1. Schedule of visits and measures

				Follow-up^{b,c}				
	Visit 1 <small>a,c</small>	Visit (Inclusion) <small>a,c</small>	Baseline (Week 0)	3 weeks	3 months	6 months	9 months	12 months
				+/- 4 days	+/- 14 days	+/- 14 days	+/- 14 days	+/- 14 days
Informed Consent Process and Informed Consent Form Signature	+							
Exclusion criteria check-up including pregnancy	+							
Randomization			+					
SURVEY								
Demographics			+					

Diet (4-day report)			+			+		+
Health history			+			+		+
Health-related quality of life			+			+		+
Hydration coaching ^d			+	+	+	+	+	
CLINICAL								
Height (cm)			+			+		+
Weight (Kg)			+			+		+
Waist circumference (cm)			+			+		+
Blood pressure (mm Hg)			+			+		+
Medications			+			+		+
BLOOD								
Blood sample	+		+	+	+	+	+	+
Fasting glucose (mmol/L)			+			+		+
Oral glucose tolerance test (OGTT) (mmol/L)			+			+		+
Fasting and 2h insulin (during OGTT) (mIE/L)			+			+		+
Fasting and 2h glucagon during OGTT) (pmol/L)			+			+		+

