Blood samples for long-term storage (biobank) are centrifuged immediately after blood draw. Then they are stored in the fridge for approximately 1-3 hours before being aliquoted and transferred (transported on ice) to the -80 degree freezer in another close-by building, approximately a 5 minute-walk from the clinical site. These samples are also transported by site staff. Assays on the biobank samples will be performed after all study subjects have completed the protocol in the same batch of reagents (includes analysis of copeptin, see above).

Blood sample measures: All routine laboratory analyses will be performed using certified methods at the University Hospital's central clinical lab, including measurement of plasma glucose (COBAS, Roche Diagnostics, Rotkreuz, Switzerland), serum insulin, serum glucagon, plasma cortisol, plasma ACTH, lipids/lipoproteins, c-reactive protein, serum creatinine, serum sodium, serum urea, serum osmolality, serum haematocrit and glycated hemoglobin (HbA1c).

Plasma copeptin will be measured in our lab (located at [name], Skåne University Hospital, Malmö) in 50 µl from fasting plasma samples stored at -80°C using a commercially available chemiluminescence sandwich immunoassay copeptin ProAVP kit with coated tubes (B.R.A.H.M.S AG, Hennigsdorf, Germany).

Procedure for OGTT: After an over-night fast (no meals or drinks after 10PM the evening before), subjects will ingest 75 g of glucose over a maximum period of 3 minutes, starting sometime between 730 and 9 AM, followed by blood sampling for glucose measurement at 30, 60 and 120 min.

Handling of urine samples: 24-hour urine samples will be collected at baseline and again at 3-weeks, and 3, 6, 9, 12 months after randomization. 24-hour urine collections follow procedures developed at the Department of Endocrinology, Skåne University Hospital, and consists of a comprehensible written instruction aimed at ensuring accurate and complete collection of urine. The procedure has been used by us in many large research studies (see for example applicant references 5 and 10). The participants start the 24-hour urine collection one day before a planned visit, and bring their container on the day of visit. For example, if their visit is on a Wednesday they start collecting urine on a Tuesday. The first urine on Tuesday morning is not collected. The

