**OR Delta 24h UVol (Baseline vs. 3 months, 6 months, 9 months and 12 months):**

- Control Group: Those with an increase in delta 24h UVol not greater than 500 mL from baseline.
- Intervention group: Those with an increase in delta 24h UVol of at least 1000 mL from baseline.

Furthermore, all individuals attending a clinic study visit (V3, V6 or V8) in a non-fasted state will be excluded from the per protocol analyses. Some other protocol deviations let to exclude patients are detailed in Section 5.1.2

Missing data

Missing data on outcomes (i.e. change of fasting glucose and the secondary cardiometabolic measures) will not be imputed, so subjects with missing data on outcome parameters will not be included in analysis of the respective outcome. For each of the outcomes, the maximum number of subjects will be included (e.g. if there are n=544 evaluable subjects for fasting glucose change, all of these will be included even if there are less evaluable subjects for any other cardiometabolic outcome parameter).

Given the randomized nature of the study, we will not perform any adjustments (which in turn can be affected by missing data on the covariates adjusted for) with three exceptions: (1) As detailed in “statistics” we will include adjustment for the baseline value of the outcome parameter in question (e.g. the change of glucose outcome will be adjusted for the baseline value of glucose). The motif of this adjustment is to minimize bias related to regression towards the mean. (2) As the randomization is stratified by sex, this covariate will be included in all outcome analyses. (3) If clinically significant/meaningful treatment group differences appear in baseline values of age, BMI or diabetes status in any outcome analysis, we will add a sensitivity outcome analysis in which we adjust for such baseline differences. Any missing values for these covariates will be imputed to obtain the same number of evaluable subjects in non-adjusted and adjusted analyses. The technique we propose is Multiple Imputation by Chained Equations (MICE) with subsequent application of Rubin’s rule to combine results from different imputations. We will base the analyses on 20-30 imputed data sets. For this analysis we will use SAS PROC MI in combination with PROC MIXED/PROC GLM and PROC MIANALYZE.

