### 5.1.3 Populations

We expect a final study sample for intention to treat analysis of at least n=544 evaluable study subjects who have completed the protocol (i.e. with at least 2 fasting glucose measurements, meaning at V3 and at either V6 or V8 or at both V6 and V8). We expect a dysbalance in the final study sample (46% intervention vs 54% control therapy) due to dysbalance in the drop-out rate between intervention and control groups.

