### 5.6.2 Analysis of primary outcome parameters

The primary analysis (intention-to-treat) will compare the between study groups (intervention vs control treatment) LS-means differences on the changes from baseline to 12 months and from baseline to 6 months in fasting plasma glucose. The main analysis will be based on a linear mixed model with fasting plasma glucose change from baseline to study visits where it is measured during the study (6 and 12 months) as dependent variable. This model produces unbiased estimates under the assumption that missing data are missing at random. The model will be adjusted (through fixed effects) for sex (because of the stratified randomization), baseline value of fasting plasma glucose, treatment, study visit and interaction between treatment and study visit. We will in the mixed regression analysis model within-patient correlation to decrease exponentially with number of days between measurements or through an AR(1) model. The choice of correlation structure specifies the variance-covariance matrix in the mixed regression model. The choice of covariance structure rests on principles of parsimony, simplicity and prior beliefs, rather than post-analysis testing. Model assumptions will be assessed through visual inspection of plots of suitable regression residuals. The estimated LS-mean differences between treatment levels for the change in fasting plasma glucose from baseline to 12 months and baseline to 6 months, the corresponding 95% confidence intervals (CIs) and p-values will be provided. The same analyses will be conducted on the imputed data set (see “Missing Data” sub-section under section 4.1) and the per protocol data set. The analyses will be conducted using SAS PROC MIXED.

Sensitivity analysis as described in Section 4.1, part “Missing Data” could be performed. Conclusions regarding the inclusion of baseline characteristics in the linear mixed model will be based on clinical significances.

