## 6.3 Handling of missing data

When running sensitivity analyses addressing unbalanced (despite randomization) distributions of baseline age, BMI or diabetes status for the ITT population, model based multiple imputation (MI) will be used for these covariates. The number of imputations will be 20-30 and we will apply MICE (Multiple Imputation by Chained Equations) to perform the imputations. Trace plots and distribution plots will be created to check the accuracy of the imputations.

Due to the balanced dropout between V2 and the baseline visit (V3) and the slightly dysbalanced dropout during the study (as indicated by preliminary data from September 2024 regarding completed V6), we will in a post-hoc analysis in an experimental fashion fill the gaps in data according to different scenarios for what the value of an unobserved measurement would have been had it been observed. In other words, we will create different data sets based on different more or less pessimistic assumptions regarding the values of unobserved measurements. These data sets can subsequently be analyzed to see what happens with treatment effects under the different scenarios.

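### Does the two-consecutive-values rule for new-onset diabetes, with fasting glucose taken only at V3, V6 and V8, need to be changed?

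*SAP*

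**What the plan says.** New-onset diabetes is a secondary outcome, listed in SAP 5.7.1 as "Diabetes incidence after baseline visit during 12 months". SAP 5.7.2 gives three routes to a case:

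- fasting: "New-onset diabetes is defined as 2 consecutive fasting plasma glucose values" of at least 7.0 mmol/L;
- OGTT: a 2-hour value of at least 11.0 mmol/L, with no repeat stated;
- outside the study: a physician's diagnosis or a prescription for diabetes, reported by questionnaire.

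Anyone with a diagnosis at or before V3 is left out of this analysis. The comparison is a logistic regression adjusted for sex.

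On timing, the Protocol (Assessment of outcome and baseline characteristics) says: "Please note that the main outcome variables are measured at baseline, 6 months and 12 months". During the OGTT, glucose ingestion is "followed by blood sampling for glucose measurement at 30, 60 and 120 min".

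On missing visits, SAP 5.1.3 makes a subject evaluable with fasting glucose "meaning at V3 and at either V6 or V8 or at both V6 and V8". SAP 4.1 (Missing data) does not impute outcomes and says that "subjects with missing data on outcome parameters will not be included in analysis of the respective outcome". SAP 6.3 adds a post-hoc analysis that will "fill the gaps in data according to different scenarios for what the value of an unobserved measurement would have been".

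**The concern.** Only two fasting values are scheduled after V3. A subject normal at V3 therefore needs both V6 and V8 raised. A first raised value at V8 does not count by this route, nor does a single raised value when the other visit was missed. Yet the outcome is named as incidence over the whole 12 months, and a subject with only one of the two visits is evaluable.

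Two classifications are not written out:

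1. Is a one-visit subject with no other positive route a non-case, or left out under the general missing-data rule? That rule names glucose change and the cardiometabolic measures. It does not say when an outcome with several routes is missing.
2. Does a raised study value at V3 make a subject a prevalent case? If not, diabetes already present at V3 could be counted as new.

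The same data could then give different case counts, and the reading might be chosen after results are seen. If attendance differs by arm, the first gap could also tilt the odds ratio.

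**Working it through.** The documents give no event rate, power or sample size for this outcome, so there is no figure to reproduce. All inputs below are assumptions unless a source is named; they show scale only.

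**Inputs.** SAP 5.1.3 expects 544 evaluable subjects. The Protocol (Outcome) expects 4-6% with diabetes, which leaves 544 × 0.94 = 511 to 544 × 0.96 = 522; 515 is used. The SD of 12-month change is 0.58 mmol/L (SAP 3.3 and 7). Within-person SD is at most 0.58/√2 = 0.41, taking all change as noise. Assumed: single values with mean 5.8 and SD 0.7, stable true means, no treatment effect.

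**V3 reading.** Simulation with 4,000,000 draws, V3, V6 and V8 each being true mean + N(0, 0.41²):

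| Reading | Flagged by fasting route | Of 515 |
|---|---|---|
| V3 ≥ 7.0 removes the subject; V6 and V8 both raised | 0.7% | about 4 |
| V3 ignored; V6 and V8 both raised | 1.5% | about 8 |
| V3 may also be the first of the pair | 2.2% | about 11 |

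About 4.3% have V3 ≥ 7.0. Of those raised at both V6 and V8, 53% were already raised at V3. Over means 5.5-6.0, SDs 0.6-0.8 and within-person SDs 0.29-0.41, the second count is 1.4-4.3 times the first. Another setting (mean 5.9, between-person SD 0.6) gives 1.1%, 2.6% and 3.7% of all subjects.

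**Capture.** Let p be the chance that a value after onset is ≥ 7.0. For post-onset means of 7.2-8.0, p = 0.687 to 1.000. With onset uniform over 12 months, the two-visit route catches 0.5p² = 0.24 to 0.50. If the other routes catch 30-70% independently, overall capture runs from 1 − 0.764 × 0.7 = 0.47 to 1 − 0.5 × 0.3 = 0.85.

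**Either-visit count.** Counting one value ≥ 7.0 at V6 or V8 flags about 5.3% of those normal at V3, or 27 of 515 against 4. About 91% of those flagged, and 94% of those added, have a true mean below 7.0 (84-99% of those added, over the grid).

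**Attendance.** Let s be the share attending both visits, f = 0.007 the fasting-route risk and o = 0.01-0.03 the other-route risk. Assume s for water/control of 85/95, 90/95 or 80/92%.

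- *One-visit subjects as non-cases:* risk = o + fs. With 80/92% and o = 0.01 the risks are 0.0156 and 0.01644, odds ratio 0.948. Range 0.95-0.99.
- *Left out unless positive by another route:* risk = [s(o+f) + (1−s)o] / [s + (1−s)o]. With 80/92% and o = 0.03 the risks are 0.0356/0.806 = 0.0442 and 0.03644/0.9224 = 0.0395, odds ratio 1.12. Range 1.03-1.12.
- *If a missed visit also loses half the other-route risk:* 0.91-0.97 and 1.02-1.06.
- *Equal attendance:* 1.00.

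**Sampling error.** With s about 0.9, events run from 511 × (0.01 + 0.0063) = 8.3 to 522 × (0.03 + 0.0063) = 19. Limits around a null odds ratio are exp(±1.96√(4/D)): 0.25-4.0 for D = 8 and 0.41-2.5 for D = 19.

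**The case for a change.** The strongest case for a change is pre-specification. Diabetes incidence is the first-listed secondary objective, the V3 reading alone can double or triple the fasting-route count, and a few sentences before database lock would settle it. The factual part stands: neither SAP 4.1 nor 5.7.2 states the two classifications outright.

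Much of the rest weakens on a close reading.

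- *V3.* The exclusion covers a diagnosis at the baseline exam as well as before it, which naturally takes in what that exam shows. The Protocol (Outcome) gives 7.0 mM as the diagnostic threshold, and SAP 6.6 classes diabetes within baseline fasting glucose status. The diabetes row under survey items in SAP 5.3 describes the sample; it is not an exclusion rule. Using V3 as the first of the pair is strained, because the restriction to after V3 closes the sentence that holds both glucose routes and SAP 5.7.1 repeats it. What stays open is whether one V3 value is enough.
- *One-visit subjects.* SAP 4.1 supplies a default, though its use for an outcome with several routes is a matter of interpretation. The 46/54 split in SAP 5.1.3 is no evidence of unequal one-visit attendance: it reflects drop-outs, who by SAP 5.8 have neither V6 nor V8.
- *Both visits required.* SAP 5.3 lists fasting glucose and, separately, fasting glucose during the OGTT. If those are two samples, a single visit could supply two values and the constraint loosens. The documents do not settle this.

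The illustrations are soft as well. Independence of the OGTT and fasting routes is unsupported, and the attendance range is not a bound. If the fasting route stood alone with 2-5% risk, and one-visit shares were 5% against 10% or 15%, or 10% against 20%, coding one-visit subjects as non-cases would give 0.88-0.95. Those risks mean 515 × 0.02 = 10 to 515 × 0.05 = 26 events, and even 26 give limits of about 0.46-2.2.

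**Conclusion.** No change to the plan follows. Requiring two raised values is a fair trade of sensitivity for specificity. With a rare outcome, cases missed equally in both arms cost events but hardly distort the odds ratio, whereas false positives pull it towards 1. An either-visit count would buy capture with additions of which about 94% have a true mean below 7.0 under the base assumptions. The 12-month label gives the observation window and does not promise that every onset is caught.

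The V3 question has a natural answer in the SAP's wording. Treatment starts only after V3 and SAP 6.3 describes drop-out before V3 as balanced, so either plausible reading adds or removes a few subjects (about 4 against 8 cases of 515) from both arms alike in expectation.

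The one-visit question is a gap that the analyst fills when deriving the variable. The calculated shifts, 0.91-1.12 in the main scenarios and 0.88 in the harshest, are far inside the sampling limits. Imputing case status for 8 to 19 events, against the general rule in SAP 4.1, would add model dependence for little gain. Readers can also see the extent: SAP 5.1.1 already promises, by arm, attendance at V6 and at V8 and the number with at least one of them. The one-visit count is then 2 × (at least one) − V6 − V8, provided that those present gave a fasting sample.

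This rests on assumed glucose distributions, event risks and attendance, none of which the documents give. The primary analysis does not use the diabetes definition.

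### The main diabetes-incidence model could adjust for baseline fasting glucose unconditionally without losing subjects; the planned sex-only model is valid, so this is a small, cheap improvement

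*SAP*

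**What the plan says.** SAP 5.7.2 analyses diabetes incidence by logistic regression on treatment arm. It argues that randomization should balance diabetes risk factors, so "the main analysis will only be adjusted for sex", the stratification factor. A sensitivity analysis then adjusts for "key diabetes risk factors at baseline (fasting glucose, diabetes status, BMI, age), if there is a clinically significant difference in these factors". No size or rule is given for that trigger. The same section states: "All individuals with a diagnosis of diabetes at or before the baseline exam (V3) will be excluded in the analysis of incidence of diabetes".

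The general rule is in SAP 4.1, under Missing data: "we will not perform any adjustments (which in turn can be affected by missing data on the covariates adjusted for) with three exceptions". The exceptions are the baseline value of the outcome concerned, sex, and a conditional sensitivity analysis when "treatment group differences appear in baseline values of age, BMI or diabetes status in any outcome analysis".

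SAP 5.1.3 describes ITT subjects as those "with at least 2 fasting glucose measurements, meaning at V3 and at either V6 or V8 or at both V6 and V8", and SAP 5.1.1 agrees. SAP 5.1.2 removes subjects who attended V3, V6 or V8 non-fasted from the per-protocol analyses only.

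**The concern.** Each continuous outcome is adjusted for its own baseline value. For incident diabetes that rule supplies nothing, because everyone in the analysis is free of diagnosed diabetes at V3. The outcome that is partly defined by a fasting glucose threshold is therefore the one whose main model has no baseline glucose term, although the value is already collected and would be expected to predict who crosses the threshold.

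SAP 4.1 gives two reasons for limiting adjustment: randomization, and missing covariate data. The second does not apply to baseline glucose in the ITT set. What is at stake is some precision on a named secondary objective, and a decision about adjustment that now depends on a judgement of imbalance made after baseline data are seen.

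**Working it through.** **1. Does adjustment lose anyone?** ITT membership needs a V3 glucose plus a value at V6 or V8 (SAP 5.1.1, 5.1.3). Every ITT subject therefore has a V3 value, and none is dropped. One qualification: non-fasted V3 attendees stay in ITT (SAP 5.1.2), so a few values may not be true fasting values.

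**2. Planned numbers.** The SAP gives no power figure for diabetes incidence, so I checked its primary-outcome figure first (SAP 3.3 and 5.1.3: SD 0.58, difference 0.14 mmol/L, two-sided 0.05, 80% power, 46:54 split).

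- Equal arms: 2 × (1.960 + 0.842)² × 0.58² / 0.14² = 269.4, so 270 per group, as stated.
- 46:54 split: (1.960 + 0.842)² × 0.58² / (0.14² × 0.46 × 0.54) = 542.4. Rounded up by arm this is 293 + 250 = 543, against 544 stated; power at 544 is 80.1%.

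For the incidence analysis, remove 5% with diabetes (the middle of the protocol's expected 4-6%): 544 × 0.95 = 517, which splits into 238 water and 279 control.

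**3. Power with and without baseline glucose.** The documents give neither an incidence nor a glucose-diabetes association, so both are assumed.

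- Model: logit P = a + ln(OR per SD) × Z + τ × T. Z is standardised baseline glucose, taken as normal; T is treatment; sex is 50:50 with no effect.
- a is solved to give control incidence 3%, 5% or 8%. τ is solved to give risk ratio 0.42, 0.71 or 1.
- 0.42 is the 58% reduction that SAP 3.3 quotes from the Finnish prevention trial. 0.71 is half of it (58/2 = 29%), by analogy with the SAP's sizing on half of that trial's glucose effect.
- OR per SD: 2, 3 or 4. Wald test at 1.96, 4,000 trials per setting.

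| True risk ratio | Sex only → sex + glucose (5% incidence, OR 3 per SD) | Over all settings |
|---|---|---|
| 0.42 | 36.6% → 39.3% | gain 1.0 to 6.6 points |
| 0.71 | 10.5% → 11.0% | gain 0.1 to 2.1 points |
| 1.00 | – | rejection 3.3-4.7% sex only, 3.6-5.0% adjusted |

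The simulation standard error of a rejection rate near 5% is √(0.05 × 0.95 / 4,000) = 0.34 points. The type I error therefore shows no inflation.

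**4. Events at 3% incidence.**

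- No effect: 517 × 0.03 = 15.5.
- 58% reduction: 279 × 0.03 + 238 × 0.0126 = 8.4 + 3.0 = 11.4.
- Chance of no water-arm event in that case: (1 − 0.0126)^238 = 0.049, about 5% of trials. Neither model can then estimate the odds ratio.

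**5. Change of estimand.** A risk ratio of 0.42 at 5% incidence is a marginal odds ratio of (0.021/0.979)/(0.05/0.95) = 0.41. Conditional on glucose, it corresponds to about 0.35-0.41 across the settings.

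**The case against.** The sex-only model is a stated choice with a stated reason, and the fallback model already contains fasting glucose. Showing that the missing-data reason does not apply leaves the randomization reason untouched. That stands: nothing here is invalid. At the 29% reduction, which is closer to the SAP's own sizing logic, power is only about 5-18% under either model. Adjustment does not change what this endpoint can show there. A sponsor could also reasonably prefer the simpler model when events are few.

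Three stronger readings are tempting, and the documents do not support them.

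- **Chance imbalance biases the sex-only result.** The SE of the baseline difference is √(1/238 + 1/279) = 0.088 SD. A two-SE imbalance would move a null odds ratio to 1.13-1.25. But ln 1.25 = 0.22 is about 0.55 of the log-odds-ratio SE of 0.405 (5% incidence in both arms), and it is part of the sampling variation that the sex-only interval already covers. Nor can the 0.14 mmol/L in SAP 3.3 serve as a limit for imbalance, because it is a treatment difference in 12-month change.
- **The covariate lists in SAP 4.1 and 5.7.2 contradict each other.** One is a general rule and the other is specific to this outcome. Diabetes status in the 5.7.2 list is merely inert: it is constant after the V3 exclusion, so its trigger cannot fire.
- **Unclear classing of one-visit subjects distorts the odds ratio.** The fasting route is "New-onset diabetes is defined as 2 consecutive fasting plasma glucose values" at or above 7.0 mmol/L, with scheduled values only at V6 and V8. A subject with one of these visits can still be a case by the OGTT or an outside diagnosis. SAP 4.1 already leaves subjects with missing outcomes out of the analysis, but does not say when diabetes status counts as missing. With assumed one-visit shares of 5% and 15% by arm, null odds ratios are 0.92-1.09, at most about 0.2 SE (ln 1.09 = 0.086; 0.086/0.405 = 0.21). With equal shares the odds ratio is 1.00. This is missing detail, not a demonstrated bias.

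**Conclusion.** The point holds as a minor improvement. The main model leaves out a collected baseline value that every ITT subject has, and ties its use to an undefined imbalance. Unconditional adjustment loses no subject. It gains about 1-7 points of power at a 58% reduction and about 0-2 points at 29%, with rejection rates at or near 5% when there is no effect. These sizes rest on assumed incidence (3-8%) and an assumed association (odds ratio 2-4 per SD); neither is in the documents. The sex-only analysis remains valid, and no bias in it has been shown.

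**What to change.** In SAP 5.7.2, include baseline fasting glucose with sex in the main logistic model unconditionally, and keep the sex-only model as supportive. Keep the diabetes definition as written.

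The cost is a few sentences before database lock and one extra model run on data already collected. The SAP should say that the main odds ratio is then conditional on baseline glucose. With 11-16 events at 3% incidence, three model terms are already many, which is a reason to add glucose alone to the main model and not BMI and age as well. The risk of no water-arm event is the same under both models.

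Two editorial changes can go in at the same time:

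- Drop diabetes status from the 5.7.2 covariate list.
- State whether the SAP 4.1 rule on missing outcomes applies to a one-visit subject who meets no diabetes criterion.
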